15.0 Potential Benefits to Participants

15.1 Potential Benefits: As this is not a treatment study, there is no direct benefit to individual participants.

16.0 Data Management

16.1 Data Analysis Plan: Means (arithmetic or geometric for log-transformed variables) and their corresponding confidence intervals will be calculated for each study condition. Results will also be tabulated separately for men and women. A linear mixed model will be fit for each outcome variable, with fixed categorical effects of group, time, and their interaction, and random subject effects to account for correlation among repeated measurements on the same subject. We expect randomization to balance groups with respect to important baseline covariates such as cigarettes smoked per day and degree of nicotine dependence; however, we will check this assumption using ANOVA and consider adjustment for imbalanced factors. Exploratory modeling of gender and race / ethnicity effects will also be performed. Model contrasts will be used to evaluate the hypotheses of the two aims, primarily that cigarettes smoked will be lower and e-cigarette use higher when menthol e-cigarettes are available (Aim 1: conditions A and C compared to B), and that these effects will be larger when menthol cigarettes are unavailable (Aim 2: condition A compared to C)

16.2 Power Analysis: The main purpose of this project is to provide initial information regarding how banning menthol in either only cigarettes or in both cigarette and e-cigarettes will influence tobacco use patterns so as to better design a subsequent study that more definitively addresses this issue. This study will also provide feasibility information regarding using an experimental marketplace for assessing this question. For this pilot study, we plan on recruiting 60 subjects and anticipate (assuming 10% dropout), that there would be 18 evaluable subjects per group. If there is a large effect, we should be able to detect it as this sample size will provide 80% power for a between-groups time-averaged effect size of 0.8, assuming two-sided alpha=0.05 and within-subject autocorrelation of 0.6.

16.3 Data Integrity: In order to ensure that data entry is correct, data collected on paper questionnaires will be entered twice with the two entries compared and any discrepancies resolved.

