2.2 Preliminary Data: Our research team has considerable experience with the methods proposed in this study and with the study population being recruited. The most relevant projects include:

2.2.1 Data demonstrating that in the event of a menthol ban in cigarettes, smokers of menthol cigarettes switch to smoking non-menthol cigarettes: In a pilot study led by [name], we asked African American menthol cigarette smokers to not smoke menthol cigarettes for a 4 week period in order to obtain information regarding how they would adjust their smoking behavior were menthol cigarettes not available (as in the event of a ban).¹⁷ No specific instructions were provided regarding how to cope with abstaining from menthol cigarettes. Of the 32 subjects who completed the study, three reported making a quit attempt with all continuing smokers switching to non-menthol cigarettes. Modest decreases occurred in cigarettes smoked per day (11.9 vs. 9.8 cigs/day; p < .001) and exhaled CO (13.4 vs. 11.1 ppm; p = .03) between the start and the end

of the 4 week period. Motivation to quit smoking was higher at the week 4 visit than at baseline (5.3 vs. 6.3 on a 10 point scale; $p = .03$). At the end of the study, subjects indicated that quitting menthol cigarettes was difficult (average score = 7.2 on a 10 point scale) but that they were supportive of banning menthol (average score = 7.1). Our finding of substantial support for a ban on menthol cigarettes is consistent with other surveys^{16, 18} and is important data since broadening support for a menthol cigarette ban among current users of menthol cigarettes would likely ease passage of such regulations. The current study would expand on these data to determine if these changes in smoking, motivation to quit smoking, and other measures assessed are either enhanced or undermined by the availability of menthol flavored e-cigarettes. This study will also provide information regarding the level of support among menthol flavored cigarette smokers of banning menthol flavoring across tobacco products.

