3.0 Study Endpoints/Events/Outcomes

3.1 Primary Endpoint/Event/Outcome: The primary outcome is the amount of each tobacco product used per week as recorded on their tobacco use surveys.

3.2 Secondary Endpoint(s)/Event(s)/Outcome(s): Secondary outcomes measured at each visit include how much of each product is obtained from the experimental marketplace, motivation and self-efficacy to quit smoking cigarettes and to quit all tobacco product use, number of quit attempts, severity of craving and withdrawal symptoms, and exhaled carbon monoxide concentrations. Support for a menthol ban and urinary cotinine concentrations will be assessed at baseline and at week 6.

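### A Gaussian mixed model, with means and intervals per condition, is a poor choice for the number of quit attempts, which the team's own pilot suggests will be sparse

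*Combined protocol and SAP*

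**What the plan says.** Section 16.1 (Data Analysis Plan) promises means, arithmetic or geometric, whose "corresponding confidence intervals will be calculated for each study condition". It then prescribes one analysis: "A linear mixed model will be fit for each outcome variable, with fixed categorical effects of group, time, and their interaction", together with "random subject effects to account for correlation among repeated measurements on the same subject". No binary, count or exact method appears for any outcome. A log transformation is mentioned only in connection with the means, with no rule for zeros.

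Section 3.2 includes, among the secondary outcomes measured at each visit, "number of quit attempts, severity of craving and withdrawal symptoms". The likely frequency of attempts can be read from section 2.2.1: "Of the 32 subjects who completed the study, three reported making a quit attempt". That pilot lasted 4 weeks. Section 2.1 gives the same result as 3 of 31. Section 9.1(d) restricts entry to smokers not currently motivated to quit.

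On the time factor, section 3.1 makes the primary outcome "the amount of each tobacco product used per week", and section 16.1 names the group contrasts, for example "Aim 1: conditions A and C compared to B". It does not list the occasions that count as levels of time. Section 16.2 bases power on a "between-groups time-averaged effect size of 0.8".

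**The concern.** A linear mixed model assumes roughly normal errors with a variance that does not depend on the mean. A count that is zero for almost everyone at almost every visit has neither property. The resulting interval for a condition is symmetric about a value close to zero, so it can include impossible negative values. If an arm has no events and its own variance is used, the interval has no width.

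This matters because section 16.2 gives the study's main purpose as supplying information for designing a later, more definitive trial. Section 2.1 also asks directly whether access to menthol e-cigarettes would make quitting more or less likely. The quit-attempt rate per condition, with an honest interval, is one of the figures a later planner would want.

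**Working it through.** **Inputs.** Pilot: 3 of 32 in 4 weeks (section 2.2.1). Study: 6 weeks with visits at weeks 2, 4 and 6 (sections 5.1 and 5.2.3). Evaluable: 60 × 0.9 / 3 = 18 per arm (section 16.2). Assumption: the pilot rate carries over to every arm and is constant over time.

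**The plan's own figure.** With a common within-subject correlation of 0.6, the mean of m measures has SD √[(1 + 0.6(m − 1))/m]. For m = 3 this is √(2.2/3) = 0.856. With 18 per group, the standardised difference is (0.8/0.856) × √(18/2) = 2.803, and power is Φ(2.803 − 1.960) = 80.0%. For m = 4 it is 81.8%. The stated 80% is reproduced by three measures, the number of post-baseline visits, although four also comes close.

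**Quit attempts per visit.**
- Two-week rate: 1 − (29/32)^0.5 = 0.048.
- Expected attempters in an arm at one visit: 18 × 0.048 = 0.86.
- Probability that an arm has none at that visit: (1 − 0.048)^18 = 0.41.

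**Quit attempts over 6 weeks.**
- Rate: 1 − (29/32)^1.5 = 0.137.
- Expected per arm: 18 × 0.137 = 2.5.
- Probability that a given arm has none: (1 − 0.137)^18 = 0.07. At least one of three arms: 1 − 0.93^3 = 0.20.
- Using 3 of 31 instead gives 14.2% and 2.5 per arm, so the discrepancy in denominators does not matter.

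**Gaussian interval for any attempt, one arm.** With x attempters of 18 and p = x/18, the interval is p ± 2.11 × √[p(1 − p)/17].

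| x of 18 | Gaussian 95% interval | Exact 95% interval |
|---|---|---|
| 0 | 0% to 0% | 0% to 19% |
| 1 | −6% to 17% | 0.1% to 27% |
| 2 | −5% to 27% | 1% to 35% |
| 3 | −2% to 36% | 4% to 41% |
| 4 | 1% to 43% | 6% to 48% |

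The lower limit is negative for x = 1, 2 or 3. At a rate of 13.7%, the binomial probability of 1 to 3 attempters is 0.70, and of none (zero width) 0.07. Coverage is 92%, against 99% for the exact interval. Pooling the variance over the three arms (51 degrees of freedom, full enumeration) gives a negative lower limit 66% of the time and 93% coverage.

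**Between-group test.** Full enumeration at 13.7% in all arms gives an actual two-sided alpha for the pooled t test of 4.5% (A and C against B, 36 v 18) and 4.4% (A against C, 18 v 18). Fisher's exact test gives 3.1% and 1.6%.

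**Sensitivity to the rate.** The chance of a negative lower limit (own-variance interval) falls to 30% at a rate of 25% and to 8% at 35%. The pilot's exact 95% interval, 2% to 25% over 4 weeks, scales to 3% to 35% over 6 weeks, or 0.5 to 6.3 people per arm.

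**The case against.** **The listed outcome is a repeated count, not one yes/no per person.** This is correct, and the 66% to 70% figures describe a six-week summary rather than the model as written. The per-visit data are sparser still. In a simulation of Poisson counts at the pilot rate (mean 0.049 per visit, equal arms, 4,000 runs), a random-intercept analysis gave negative lower limits for 85% of arm-visit intervals. Coverage stayed at 95% to 96%, and the test of A and C against B rejected in 3.8% of runs. So the fault in form remains, but coverage need not be poor.

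**The rate may be higher here.** E-cigarettes and medicinal nicotine are supplied in every arm, and section 2.2.2 reports a higher rate of quit attempts in an earlier marketplace study. The no-ban arm could be lower. The rate is unknown, and at 25% to 35% the problem largely goes away.

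**The harm is modest.** This stands: it is a secondary outcome in a pilot, and a later planner given x of 18 could compute an exact interval at once. A pooled model also avoids the zero-width interval unless every arm is empty.

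**A stronger reading for e-cigarette use.** Exclusion 9.2(e) removes people who use other tobacco more than 9 times a month. A reader might infer that baseline e-cigarette spread is tightly bounded, and that a constant-variance model with baseline as a level of time would give intervals that are too narrow. The documents do not support that as a finding. A monthly cap does not limit any single week. It counts occasions rather than amount, and it rests on self-report at screening. The inflation also needs several modelling choices together that section 16.1 does not make, and it disappears under the time-averaged contrast that section 16.2 names. What remains is that the levels of time are not listed.

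**Conclusion.** The point holds for quit attempts and is modest in size. At the pilot's rate the planned model would be fitted to data in which about 95% of person-visits are zero, and most Gaussian intervals for an arm would extend below zero. Coverage of the six-week any-attempt interval would be 92% to 93% instead of 95%. These figures rest on carrying a single-group, 4-week rate over to three marketplace arms at a constant hazard. The scaled range of 3% to 35% runs from worse than this to almost no problem.

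A reader might also infer that the quit-attempt comparison has excess false positives. It does not: actual alpha is slightly below 5%. For e-cigarette use, only a gap in wording is established.

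**What to change.** In section 16.1, exempt the number of quit attempts from the linear mixed model. Report any attempt by week 6 in each condition with an exact binomial interval, and compare conditions by an exact test. Use logistic regression only if every arm has events, because an empty arm has no finite ordinary logistic estimate. Keep the listed count by tabulating the number of attempts by condition and visit, with a count model if there are enough events.

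As a minor clarification, state that the time factor means the post-baseline occasions and that the Aim 1 and Aim 2 contrasts are averaged over them. This agrees with the stated power.

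The cost is a few sentences and a little programming, with no new data. The exact test is conservative (3.1% and 1.6% against 4.5% and 4.4%), so some power is given up on a secondary outcome for which the study was not sized.

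### Baseline adjustment hangs on an ANOVA balance check instead of being fixed in advance, and baseline's place in the mixed model is not stated

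*Combined protocol and SAP*

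**What the plan says.** Section 16.1 uses one model form throughout: "A linear mixed model will be fit for each outcome variable", "with fixed categorical effects of group, time, and their interaction", plus random subject effects. It expects randomization to balance "important baseline covariates such as cigarettes smoked per day and degree of nicotine dependence", and then says "we will check this assumption using ANOVA and consider adjustment for imbalanced factors". It gives no threshold for the check, no closed list of factors and no form of adjustment.

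It does not say whether week 0 is a level of time, a covariate or the base of a change score. Section 3.1 sets the outcome unit: "The primary outcome is the amount of each tobacco product used per week as recorded on their tobacco use surveys". Section 3.2 adds outcomes with one follow-up only: "Support for a menthol ban and urinary cotinine concentrations will be assessed at baseline and at week 6". Section 16.2 claims "80% power for a between-groups time-averaged effect size of 0.8, assuming two-sided alpha=0.05 and within-subject autocorrelation of 0.6", with 18 evaluable subjects per group.

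The data for adjustment are already collected. Daily surveys start once eligibility is confirmed (5.2.1), and tobacco use since screening is determined at the baseline visit (5.2.2).

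**The concern.** In a randomized trial, baseline adjustment reduces variance according to the correlation between baseline and outcome. Whether the arms differ at baseline has no bearing on that gain. A balance test at the 5% level flags about 5% of properly randomized trials per covariate, so a rule tied to it nearly always forgoes the gain.

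Chance differences too small to be flagged also pass into the estimate. With 18 per arm, the standard error of a two-arm baseline difference is sqrt(2/18) = 0.33 SD. At r = 0.6, a one-standard-error imbalance shifts the unadjusted comparison by 0.6 x 0.33 = 0.20 SD, a quarter of the 0.8 SD design effect. If the third arm lies midway, the ANOVA statistic is 18 x 2 x (0.333/2)^2 / 2 = 0.5 on 2 and 51 degrees of freedom (p about 0.6), and nothing is flagged.

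Baseline's role is a second gap. Because one model form serves every outcome, and cotinine and ban support have only a baseline and a week 6 value, more than one reading is possible. Modelling post-baseline values alone ignores baseline. Treating baseline as a time level and contrasting change from it subtracts all of the baseline difference, which over-corrects when r is modest. The pilot's estimates are meant to plan a later study, so the width of their intervals matters.

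**Working it through.** **Inputs.** From 16.2: 18 per group, effect 0.8 SD, two-sided alpha 0.05, correlation 0.6. From 5.2.3: three follow-up visits; the weekly primary outcome gives six values over six weeks. Assumed, because the plan does not say: the 0.6 is exchangeable among follow-ups, variances are equal, and r is the correlation of baseline with each follow-up.

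**The plan's own figure.** The variance of a mean of K follow-ups, in SD² units, is v = (1 + (K-1) x 0.6)/K. This is 0.7333 for K = 3 and 0.6667 for K = 6. With K = 3, z = 0.8/sqrt(0.7333 x 2/18) = 2.80, and power = Φ(2.80 - 1.96) = 80.0%. The stated power is reproduced with no baseline information. The same calculation for Aim 1 (36 against 18) gives 89.9%.

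**Variance under each approach.**
- Post-baseline mean, unadjusted: v
- Baseline as covariate: v - r²
- Change from baseline: v + 1 - 2r

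Loss of precision is 1 - (v - r²)/(variance of the approach used). The covariate costs a factor 1 + 1/(54 - 3 - 2) = 1.0204. *Net* means after multiplying v - r² by that factor.

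| Loss against fixed adjustment | r = 0.1 | 0.2 | 0.4 | 0.6 |
|---|---|---|---|---|
| v - r², K = 3 | 0.7233 | 0.6933 | 0.5733 | 0.3733 |
| Never adjusted, K = 3 | 1.4% | 5.5% | 21.8% | 49.1% |
| Same, net | -1% | 4% | 20% | 48% |
| Never adjusted, K = 6 | 1.5% | 6.0% | 24.0% | 54.0% |
| Change from baseline, K = 3 | 52.8% | 48.0% | 38.6% | 30.0% |
| Adjusted if ANOVA p<0.05, K = 3 (simulated, net) | -0.5% | 2.8% | 17.0% | 42.4% |
| Adjusted if ANOVA p<0.20, K = 3 (simulated, net) | -0.3% | 1.8% | 11.0% | 30.8% |

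The triggered rows come from 200,000 simulated trials per setting, using the Aim 1 contrast and one covariate. Both thresholds are assumptions.

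As a reduction in standard error, sqrt((v - r²)/v) for K = 3 gives 0.7%, 2.8%, 11.6% and 28.7%, before the degree-of-freedom cost. The net gain is zero at r = sqrt(0.7333 x (1 - 1/1.0204)) = 0.12.

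**If the 0.6 means AR(1)**, with baseline one step before the first follow-up:
- K = 3: 0.680 falls to 0.526, a 22.6% loss.
- K = 6: 0.468 falls to 0.411, a 12.1% loss, or a standard error about 6% smaller.

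**Power at 0.8 SD by reading** (K = 3, r = 0.6, pairwise):
- Post-baseline only: 80.0%
- Change from baseline: 90.8%
- Covariate: 97.5%
- Baseline averaged in as a fourth time level (effect diluted to 0.75 x 0.8 = 0.6, variance 0.70): 57.6%

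**Type I error.** In a separate simulation (40,000 trials, pairwise contrast, r = 0.6), the p<0.05 rule applied mechanically gave 4.1%. Picking the more favourable of the adjusted and unadjusted results gave 8.3%.

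**Indirect evidence on r.** Section 2.2.1 reports 11.9 against 9.8 cigarettes per day, p < .001, with 32 completers. If that is a paired t test, t exceeds 3.633 on 31 degrees of freedom. The SD of change is then at most 2.1 x sqrt(32)/3.633 = 3.27. With equal SDs at both times, r is at least 1 - 3.27²/(2 SD²), which is 0.41, 0.67 or 0.79 for an assumed SD of 3, 4 or 5.

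**The case against.** The strongest reply is that this is a pilot with adequate stated power, and that the gain is of unknown size. Several parts of that reply stand:

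- **r is not given.** The bound from the earlier pilot needs a paired test, an assumed SD and equal variances. No e-cigarettes were supplied there. Section 2.3 cites studies with e-cigarettes in which median cigarettes per day fell by 80% and 23% to 36% quit entirely; many near-zero values could lower r. Section 16.1 also allows log-transformed outcomes, for which the raw-scale gains need not hold.
- **Precision losses look larger than interval widths.** At r = 0.4 the standard error falls by about 12%, and under AR(1) with weekly values by about 6%.
- **Section 16.2 points to post-baseline values for the primary outcome.** Its 80% is reproduced that way, although the number of repeats has to be inferred. The change-from-baseline row is therefore the less supported reading, and the never-adjusted and triggered rows are the relevant ones.
- **The simulated trigger is not exactly the plan's rule**, which has no threshold and names more than one factor.
- **E-cigarette use gains little.** Section 9.2 excludes regular users of other tobacco, so baseline use is probably near zero.

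None of this supports the ANOVA trigger. It bears on how much is lost, not on whether a fixed rule is better. Below r of about 0.12 fixed adjustment costs at most about 2% of variance; above it, it gains. The pilot's purpose of informing a later design is a reason to want tighter estimates from the same 54 people.

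**Conclusion.** The point holds and should be changed, as a matter of efficiency and conditional bias rather than validity. The 80% power claim is correct, and a mechanically applied check does not inflate type I error; a risk arises only if the discretion to consider adjustment were used to choose between results.

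For cigarette use, with exchangeable correlation 0.6 and 18 per arm, the plan as written loses from nothing at r = 0.1 to about 17% of precision at r = 0.4 and 42% at r = 0.6 under an assumed p<0.05 trigger. With p<0.20 the last two are 11% and 31%. If adjustment is never made, they are 20% and 48%, net. AR(1) correlation gives smaller losses. Confidence in the direction is high for any r above about 0.12; confidence in the size is moderate, because r is not stated.

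**What to change.** In 16.1, replace the ANOVA trigger with a fixed rule such as:

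> *For cigarette use, mean daily cigarettes from the surveys completed before the baseline visit (the screening report if none were completed) enters the model as a covariate whatever the observed balance. Only post-baseline times are responses.*

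A baseline-constrained mixed model is an acceptable alternative, but the plan should name one of the two. A mean per day is needed because the screening-to-baseline interval varies (8.0). If the outcome is log-transformed, state the scale of the covariate as well.

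List the other outcomes to which the rule applies: those with a baseline value expected to predict follow-up and recorded before subjects learn their condition and receive products. For cotinine and ban support this becomes a week 6 ANCOVA. Say whether nicotine dependence is a second fixed covariate or only descriptive. Claim no precision gain for e-cigarette use, and tabulate baseline characteristics without tests.

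The cost is one or two sentences for the core rule and one degree of freedom per covariate, about 2% of variance with 54 people. No new data are needed.

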1.0 Objectives

1.1 Objective: The objective of this study is to obtain preliminary information regarding how a menthol ban that either exempts or includes e-cigarettes is likely to affect overall tobacco use

1.2 Specific Aims: The following specific aims will be pursued:

Aim 1: Determine the impact of the availability of menthol flavor in e-cigarettes on overall tobacco product use patterns

We hypothesize that menthol cigarette smokers will smoke fewer cigarettes, vape more e-cigarettes, have higher motivation to quit smoking and be more supportive of a ban on menthol cigarettes when given the option of using menthol flavored e-cigarettes than when no such option is present.

Aim 2: Determine if the impact of the availability of menthol flavor in e-cigarettes on tobacco use behavior is moderated by a ban on menthol flavor in cigarettes

We hypothesize that the impact of menthol flavored e-cigarette availability on the above measures will be greater during a simulated ban on menthol cigarettes than if smokers can continue smoking menthol cigarettes.

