have found that over 12% of adults have tried e-cigarettes and that 5.5% of all adults and 8.9% of young adults use e-cigarettes either every day or on some days.^{5, 6} Sales of e-cigarettes for 2016 are estimated at approximately \$1.6 billion and some estimates project that e-cigarette sales may overtake cigarette sales within 10 years.^{7, 8} Almost every commonly used brand of e-cigarette is currently available in menthol flavor⁹ and data from surveys suggest that as many as 30% of e-cigarette users prefer menthol flavored products with over 12% of e-cigarette users stating that they use e-cigarettes “because they come in menthol flavor.”¹⁰⁻¹³ However, there is little information assessing if the availability of menthol flavorant in e-cigarettes affects smoking behavior in the context of a ban on menthol flavorant in cigarettes.

With the recent extension of FDA authority to additional categories of tobacco products including e-cigarettes,¹⁴ the ability to enact regulations regarding the availability of flavorants (including menthol) will extend to these other categories of tobacco products as well. Although surveys of menthol smokers suggest that a substantial number would attempt to quit smoking if menthol cigarettes were unavailable,^{3, 15, 16} our preliminary data found that relatively few in fact made a cessation attempt (only 3 out of 31 subjects). However, it is not known if access to menthol flavored e-cigarettes would increase the likelihood of menthol smokers quitting smoking entirely in the event of a ban since they have an alternate menthol product available or conversely if likelihood of quitting would decrease with smokers opting to use a combination of non-menthol cigarettes and menthol flavored e-cigarettes. The former would support exempting menthol e-cigarettes from a menthol ban whereas the latter would support enacting a menthol ban that would include all tobacco products. Among the numerous research needs regarding e-cigarettes identified in an NIH sponsored workshop are the needs to evaluate the effects of flavorants, biomarkers of exposure, and patterns of use.¹⁴ The purpose of the current study is to obtain initial data regarding how menthol flavoring in e-cigarettes affects tobacco use patterns in menthol cigarette smokers in order to plan future studies that more definitely assess if regulatory policy regarding menthol flavoring should be uniform across products.

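### Neither planned contrast isolates its aim: A and C against B mixes the menthol-cigarette ban into the e-cigarette effect, and A against C is not a test of moderation

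*Combined protocol and SAP*

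**What the plan says.** Section 4.1 defines three marketplaces. In A, menthol is removed from cigarettes only. In B, it is removed from cigarettes and e-cigarettes. In C, it is removed from neither.

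Aim 1 (section 1.2) asks what menthol e-cigarette availability does to product use, comparing smokers "when given the option of using menthol flavored e-cigarettes than when no such option is present". Aim 2 asks whether that effect "will be greater during a simulated ban on menthol cigarettes than if smokers can continue smoking menthol cigarettes".

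Section 16.1 turns these into model contrasts. For Aim 1, "cigarettes smoked will be lower and e-cigarette use higher when menthol e-cigarettes are available (Aim 1: conditions A and C compared to B". For Aim 2, "these effects will be larger when menthol cigarettes are unavailable (Aim 2: condition A compared to C". It gives no weights for the Aim 1 contrast and does not say whether A and C are pooled or each compared with B. It also plans means for the arms, "and their corresponding confidence intervals will be calculated for each study condition".

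Section 16.2 claims "80% power for a between-groups time-averaged effect size of 0.8, assuming two-sided alpha=0.05 and within-subject autocorrelation of 0.6", with 18 evaluable subjects per group.

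**The concern.** Set out by the two menthol factors, the design is:

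| | Menthol e-cigarettes available | Not available |
|---|---|---|
| Menthol cigarettes banned | A | B |
| Menthol cigarettes available | C | no arm (D) |

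A against B changes one factor. C against B changes two, so bringing C into the Aim 1 contrast brings in the effect of the cigarette ban. Moderation is a difference of differences and needs all four cells; A against C uses two.

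Both contrasts can be rescued by assuming B = D, that is, that a menthol-cigarette ban changes nothing when menthol e-cigarettes are unavailable. The documents do not state this, and without D the data cannot test it. The team's own pilot (section 2.2.1) gives reason for doubt: cigarettes per day fell after menthol cigarettes were stopped, although that comparison was uncontrolled.

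At stake is what the pilot passes to the next study. If the ban alone lowers smoking, Aim 1 understates the e-cigarette effect and Aim 2 can report moderation where there is none.

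**Working it through.** **Inputs.** From 16.2: 18 evaluable per arm, effect 0.8 SD, two-sided alpha 0.05, correlation 0.6. From 5.2.3: three post-baseline visits. From 2.2.1: 11.9 to 9.8 cigarettes/day. Assumed, because the documents give none: the outcome SD, and the A−C and B−D gaps.

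**The plan's own figure.** The variance of a three-visit average is (1 + 2×0.6)/3 = 0.733 SD².

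- 18 vs 18: SE = √(0.733×2/18) = 0.2854 SD. Normal-approximation power at 0.8 SD is Φ(0.8/0.2854 − 1.96) = 80.0%, which is the stated value.
- 36 vs 18: SE = √(0.733×(1/36 + 1/18)) = 0.2472 SD, giving 89.9%.

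So 16.2 powers a two-arm comparison, not the pooled one.

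**Algebra.**

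- Pooled Aim 1, equal weights: (A+C)/2 − B = (A−B) + (C−A)/2. This is the effect under a ban only if A = C, which the Aim 2 hypothesis expects to be false.
- Against the average effect over ban status, (A+C)/2 − (B+D)/2, the pooled contrast is off by (D−B)/2. It is right only if B = D.
- Pairwise reading: A−B is clean, but C−B = (A−B) + (C−A) carries the whole gap.
- Moderation: (A−B) − (C−D) = (A−C) − (B−D). So A−C is moderation plus (B−D).

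**Size.** Noncentral t, 54 − 3 = 51 df. Menthol e-cigarettes lower smoking by 0.8 SD in both ban states (no moderation), and the cigarette ban alone lowers it by the amount shown:

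| Ban effect (SD) | A vs B | Pooled Aim 1 | C vs B | A vs C significant, no moderation |
|---|---|---|---|---|
| 0 | 79% | 89% | 79% | 5% |
| 0.2 | 79% | 79% | 54% | 11% |
| 0.4 | 79% | 66% | 28% | 28% |
| 0.8 | 79% | 36% | 5% | 79% |

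The primary outcome is weekly use. With six weekly values the variance factor is (1 + 5×0.6)/6 = 0.667. At a 0.4 SD ban effect, A vs B then has 82.2%, pooled 70.5%, and A vs C is falsely significant 30.3% of the time.

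If A−B is truly zero and the A−C gap is 0.4 SD, the pooled test rejects 12% of the time (three visits).

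**Break-even.** Let r be the A−C gap as a fraction of the A−B effect, with A showing the larger reduction. Pooling has more power than A vs B only while 1 − r/2 > 0.2472/0.2854 = √0.75, so r < 0.27.

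**Illustration in cigarettes.** The pilot fall is 11.9 − 9.8 = 2.1 per day. If B−D were −2.1, the pooled contrast would understate the average reduction by 2.1/2 = 1.05 per day. A vs C would show 2.1 per day with no moderation, significant 44 / 30 / 15 / 11% of the time at assumed SDs of 4 / 5 / 8 / 10.

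**The case against.** The best defence is that the policy question survives. Section 1.1 asks "how a menthol ban that either exempts or includes e-cigarettes is likely to affect overall tobacco use", and A vs C, B vs C and A vs B answer that without a fourth arm. The model has a categorical group effect and arm means are planned, so the clean comparison can be had from the planned analysis. The study is a pilot. This stands, and it limits the point to how contrasts are matched to aims.

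Second, 16.1 does not say that A and C are pooled. If they are compared with B separately, A vs B is already in the plan. That also stands, but C vs B would still count as Aim 1 evidence while carrying the full A−C gap, and Aim 2 is unaffected by the choice of reading.

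Third, the sizes are hypothetical. A 0.8 SD ban effect is as big as the effect 16.2 calls large. At SDs of 4 to 10, the pilot fall is 2.1/4 = 0.53 to 2.1/10 = 0.21 SD, so the last row of the table lies beyond it. At 0.2 SD, pooling loses nothing against A vs B. The pilot was also uncontrolled, enrolled African American smokers only, and describes no e-cigarette marketplace. All fair: the 0 to 0.4 SD rows are the more useful guide, and the pilot only illustrates scale.

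Fourth, if the ban lowers smoking, the Aim 1 error for cigarettes runs against the hypothesis. True, but the Aim 2 error then runs in its favour. For e-cigarette use the algebra is the same, but the documents give nothing from which to judge the direction.

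**Conclusion.** The concern holds and should be fixed. Aim 2 is the firmer part: under any reading, A vs C equals moderation plus (B−D), so it tests moderation only if B = D. For Aim 1, the pooled contrast is off by half the A−C gap (target: effect under a ban) or half the B−D gap (target: average effect), in either direction.

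For assumed ban effects of 0 to 0.4 SD and a 0.8 SD e-cigarette effect, pooled power runs from 89% down to 66% while A vs B stays at 79%, and false moderation signals rise from 5% to 28%. These figures rest on 18 per arm, three visits, correlation 0.6, equal weights and assumed gaps; the algebra rests on none of them except the equal weights. The consequence is limited because this is a pilot and A vs B can be taken from the planned model.

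**What to change.** In 16.1:

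- Name A vs B, from the same mixed model, as the Aim 1 contrast for each product's use, and state that it estimates the effect of menthol e-cigarette availability under a menthol-cigarette ban. That matches the question in 2.1, whether "access to menthol flavored e-cigarettes would increase the likelihood of menthol smokers quitting smoking entirely in the event of a ban".
- Report C vs B as the combined effect of banning menthol in both products.
- If the pooled contrast is kept, give its weights, label it supportive and state its assumption: A = C for the effect under a ban, or B = D for the average effect.
- Describe A vs C as the effect of the menthol-cigarette ban when menthol e-cigarettes are available, and say that it tests moderation only if B = D.

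In 1.2, align the wording of Aims 1 and 2, so that Aim 2 no longer promises a moderation test without that assumption.

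**Cost.** Wording only; no new arm, subjects or data. Aim 1 becomes narrower. A vs B uses 36 rather than 54 subjects, so its SE is 0.2854/0.2472 = 1.15 times that of pooling, with 79% rather than 89% power if A and C are truly equal.

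A direct moderation test belongs in the follow-on study. With D added, 80% power for a 0.8 SD interaction needs 4×0.733×(1.960 + 0.842)²/0.8² = 36 per cell (normal approximation, three visits). That is 144 evaluable, or 144/0.9 = 160 recruited.
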